### **10.3.2 Analysis of Laboratory Data by Week 12**

The laboratory data will be summarized by the "as treated" treatment groups (Upadacitinib 15 mg QD, Upadacitinib 30 mg QD, and combined placebo groups) and overall.

#### **10.3.2.1 Assessment of Mean Change from Baseline and Percentage Change from Baseline in Clinical Laboratory Variables**

Analyses of mean change from baseline in continuous hematology, chemistry, and urinalysis variables which are measured longitudinally will be performed by visits and by "as treated" treatment group. For each change from baseline analysis, the following summary statistics will be presented for each treatment group: sample size, baseline mean, visit mean, and the mean, standard deviation, and median of the changes from baseline. An ANOVA model with treatment as a factor will be used to test statistical significance for the change from baseline mean among different treatment groups.

In addition, similar analyses will be conducted for percentage change from baseline in LDL, HDL and cholesterol.

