**Discontinuation of Study Drug and Continuation of Study Participation Period 1 and Period 2)**

Subjects may discontinue study drug treatment but may choose to continue to participate in the study (refer to Section 5.4.1 for additional details). Subjects who prematurely discontinue study drug should complete a Premature Discontinuation visit (PD visit) as soon as possible, preferably within 2 weeks, and preferably prior to initiation of another therapy. To minimize missing data for efficacy and safety assessments, subjects who prematurely discontinue study drug treatment should continue to be followed for all regularly scheduled visits as outlined in the Activity Schedule ([Appendix D](#) and [Appendix F](#)), unless subjects have decided to discontinue study participation entirely (withdrawal of informed consent). Subjects should be advised on the continued scientific importance of their data even if they discontinue treatment with study drug early. Following discontinuation of study drug, the subject should be treated in accordance with the investigator's best clinical judgment irrespective of whether the subject decides to continue participation in the study. As the subject has discontinued study drug, all rescue and efficacy driven discontinuation criteria no longer apply (e.g., CDAI calculation at Week 24, 20% TJC/SJC calculation for PD). If at any point a subject no longer wants to provide assessments (withdrawal of informed consent) following discontinuation of study drug, a second (PD visit) is not required.

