## **5.2 Analysis Windows**

### **Definition of Study Days (Days Relative to the First Dose of Study Drug)**

Study Days are calculated for each collection date relative to the date of the first dose of study drug. It is defined as the number of days between the date of the first dose of study drug and the collection date. Study days are negative values when the collection date of interest is prior to the first study drug dose date. Study days are positive values when the collection date of interest is on or after the first study drug dose date. The day of the first dose of study drug is defined as Study Day 1, while the day prior to the first study drug dose is defined as Study Day -1 (there is no Study Day 0). Study days are used to map actual study visits to the protocol-specified study visits.

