### **Definition of Analysis Windows**

The following rules will be applied to assign actual subject visits to protocol-specified visits. For each protocol-specified study visit, a target study day will be identified to represent the corresponding visit along with a window around the target day. Windows will be selected in a non-overlapping fashion so that a collection date does not fall into multiple visit windows. If a subject has two or more actual visits in one visit window, the visit closest to the target day will be used for analysis. If two visits are equidistant from the target day, then the later visit will be used for analysis.

The visit window and the target study day for each protocol-specified visit in Period 1 are displayed in Table 1 and Table 2 (depending on the different visit schedules of different endpoints). Visit windows for protocol-specified visits in Period 2 are defined similarly.

**Table 1. Analysis Windows for Efficacy Analysis for Period 1 (for ACR Components and Morning Stiffness) and Safety Analysis for Period 1 (for Labs and Vital Signs)**

Protocol Specified Visit Week	Lower Bound	Target Day	Upper Bound
Baseline	-99	1 a	1
1	2	8	11
2	12	15	22
4	23	29	43
8	44	57	71
12	72	85	first dose date from Week 12 dispensed kit
16	first dose date from Week 12 dispensed kit + 1	113	127
20	128	141	155
24	156	169	first dose date of Period 2

a. Day of first dose of study drug.

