## **10.2 Analysis of Adverse Events**

A treatment-emergent Adverse Event (TEAE) is defined as an adverse event with an onset date that is after the first dose of study drug, and no more than 30 days of the drug after the last dose of study drug.

Events where the onset date is the same as the study drug start date are assumed to be treatment-emergent, unless the study drug start time and the adverse event start time are collected and the adverse event start time is prior to the study drug start time. If an incomplete onset date was collected for an adverse event, the event will be assumed to be treatment-emergent unless there is other evidence that confirms that the event was not treatment-emergent (e.g., the event end date was prior to the study drug start date).

Adverse event data will be presented by SOCs and PTs using MedDRA Version 19.1 or most up to date version. All adverse event tables will be sorted in alphabetical order by SOC and PT and descending percentages for each treatment group.

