#### **10.3.2.2 Assessment of Shift from Baseline in Clinical Laboratory Variables**

The baseline and post-baseline laboratory observations will be categorized as Grade 1, Grade 2, Grade 3, and Grade 4 according to OMERACT criteria (Rheumatology Common Toxicity Criteria v.2.0). For creatine phosphokinase and creatinine, NCI CTC criteria will be used.

For each laboratory variable, shift tables will be generated that cross tabulate the subjects as deemed appropriate by "as treated" treatment group:

- Category of the baseline value versus category of the final value.
- Category of the baseline value versus maximum category.
- Category of the baseline value versus minimum category.

Note that the minimum/maximum category is used, rather than the category of the minimum/maximum value. The two may be different due to variation in the reference range.

No statistical tests will be performed for this analysis.

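### Long-term by-visit means of laboratory values and vital signs have no limit after the last dose, so values taken off drug count in the upadacitinib group means

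*SAP*

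**What the plan says.** **How values reach visits.** SAP 5.2 states: "Study days are used to map actual study visits to the protocol-specified study visits". Table 1 gives the Period 1 windows and names laboratory values and vital signs among the data it covers. Period 2 windows are said to be built in a similar way. Within a window the selection rule is: "If a subject has two or more actual visits in one visit window, the visit closest to the target day will be used for analysis". Being on drug is not a condition.

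**Who still supplies values.** Protocol 5.1 says that "subjects who prematurely discontinue study drug treatment should continue to be followed for all regularly scheduled visits". The note to Appendix D exempts them only from dispensing, PK samples and optional research samples, so laboratory tests and vital signs continue. Treatment after stopping is left to the investigator. A follow-up visit about 30 days after the last dose also collects both, with exceptions noted below.

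**Which group they count in.** SAP 5.1 sets the as-treated group by the treatment taken for most of the exposure time, so stopping does not change the label.

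**What is summarised.** For laboratory values, SAP 10.3.2.1 and 10.3.3.1 share the wording "Analyses of mean change from baseline in continuous hematology, chemistry, and urinalysis variables which are measured longitudinally will be performed by visits". SAP 10.3.3.1 and 10.4.3 give mean change by visit and as-treated sequence. The only censoring, there and in SAP 10.1, is at the switch from 30 mg to 15 mg.

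**What the SAP does elsewhere.** Treatment-emergent adverse events must start "no more than 30 days of the drug after the last dose of study drug" (SAP 10.2). In SAP 9.1.2, the observed-cases analysis drops values after discontinuation, and the as-observed analysis expressly keeps them.

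**The concern.** A reader takes a by-visit mean for an upadacitinib sequence as describing subjects on upadacitinib at that visit. Under the written rules it mixes values on drug with values taken weeks or years after the last dose, possibly under another therapy.

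Two features make this matter. Stopping can depend on the outcome: Protocol 6.1.7 (Table 4) ends study drug for some confirmed neutrophil counts and for some unexplained or unresolved transaminase elevations. The same table withholds drug until values recover, which presumes that effects reverse off drug. The subjects whose recovered values enter the mean may therefore include those with the clearest laboratory effect.

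The laboratory means and the adverse event tables for the same dose would also rest on different exposure periods, without the SAP saying so.

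**Working it through.** **1. The plan's own figures.** Neither document gives a figure for laboratory or vital-sign summaries. The only stated result that uses dropout is the power in SAP 4.3. With 150 × 0.9 = 135 per group and two-sided α = 0.025, the pooled normal approximation gives 88.3% for ACR20 (27% v 47%) and 89.4% for LDA (12% v 29%). Both agree with the stated 90% or so, and that calculation is not in dispute.

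**2. Does the rule admit off-drug values?** Table 1 prints Period 1 windows only, so they show the mechanism:

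- Last dose Day 28, subject stays in the study and attends Week 12 on Day 85: 85 − 28 = 57 days off drug, used as that subject's Week 12 value.
- Last dose Day 55, 30-day follow-up sample taken: 55 + 30 = Day 85, exactly the Week 12 target.

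Targets follow 7 × week + 1 (Week 12 = 85, Week 24 = 169). In Period 2, Week 60 is therefore Day 421 and Week 72 is Day 505. A subject whose last dose is on Day 421 and who keeps attending supplies a Week 72 value 505 − 421 = 84 days off drug. By Week 260 the gap is 260 − 60 = 200 weeks. If this subject never switched dose, no censoring rule applies.

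**3. Size.** Let f be the share of contributing subjects off drug at a visit and r the share of the drug effect that has reversed. If those who stopped would have had the average on-drug effect, the mean shows 1 − f × r of it. The values of f and r below are assumptions.

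| f | r = 25% | r = 50% | r = 100% |
|---|---|---|---|
| 5% | 98.8% | 97.5% | 95.0% |
| 10% | 97.5% | 95.0% | 90.0% |
| 15% | 96.3% | 92.5% | 85.0% |

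**4. What f could be.** SAP 9.1.2 expects 10–15% discontinuation in RA trials generally. That is a ceiling for f at Week 12, because subjects who leave the study supply no later scheduled values. If D is the proportion who have stopped and s the share of them still measured, f = D·s / (1 − D + D·s). With s = 50% (assumed):

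- D = 10%: 0.05 / 0.95 = 5.3%
- D = 15%: 0.075 / 0.925 = 8.1%

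Only s = 100% gives f = 10–15%. For Period 2 the documents give neither D nor s.

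**The case against.** **The Week 12 analysis is closed.** SAP 11.1 says Period 1 reporting was completed under version 2.0 and that version 3.0 governs only future long-term reporting. This stands. A reader might infer that reported Week 12 safety results must now change, but the documents support at most a sensitivity re-run. Shift tables appear only in SAP 10.3.2.2, so they belong to that completed work.

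**Not every safety output is diluted.** A reader might extend the point to all shifts and counts. An added off-drug value cannot erase an on-drug abnormality from a maximum- or minimum-category shift, or from a Week 12 count of potentially clinically significant values. It can only add a misattributed one. The shift defined as "Category of the baseline value versus category of the final value" is the one that can be diluted. Long-term significant-value and liver-elevation counts are assigned by the treatment received at the time (SAP 10.3.3.2, 10.3.3.3, 10.4.3), and affected subjects are listed with their full course. A severe on-drug value is therefore not hidden.

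**The Week 24 window is not a leak for completers.** Its upper bound is a Period 2 first dose that some completers never take, so a reader might think their follow-up sample replaces Week 24. Their last dose is the day before the visit (Day 168), so follow-up falls near Day 198, 29 days from target. The rule that "the visit closest to the target day will be used for analysis" selects the Week 24 visit unless its value is missing.

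**The follow-up sample is not always available.** Under Protocol 5.1, after early discontinuation it may be a telephone call without tests. It does not apply to subjects who stay in the study and attend a visit at least 30 days after the last dose. This stands, so the main source of off-drug values is the scheduled visits of subjects who stay.

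**Using post-drug values may be deliberate.** Follow-up continues in order to limit missing safety data, and which values to use is partly a choice of estimand. That is fair, but the SAP does not state such a choice for these means, although it does for efficacy. It is also true that removing off-drug values leaves late means resting on those who stayed on drug, and does not recover the abnormality that led to stopping.

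**Conclusion.** The point holds for the long-term by-visit mean changes in laboratory values and vital signs. Applied as written, the SAP 5.2 windows put off-drug values into as-treated sequence means, and no rule in SAP 10.1, 10.3.3.1 or 10.4.3 removes them except at the dose switch.

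The understatement is about f × r of any effect that reverses off drug. At Week 12, 10–15% is the most the SAP's own discontinuation figure allows. It requires every subject who stops to keep attending and to have reversed fully. A reader might infer a much larger attenuation late in Period 2, since f can grow while follow-up runs to Week 260, but the documents give no figure to support one. The direction is also an inference: it rests on reversal off drug, and other therapy after stopping could move values either way.

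These summaries are descriptive, so no test is affected. This should be corrected before the remaining long-term reporting. It does not call the completed primary analysis into question.

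**What to change.** In SAP 5.2, 10.3.3.1 and 10.4.3:

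- Restrict by-visit means to values collected no more than 30 days after the last dose of study drug, matching the treatment-emergent adverse event limit. Keep the existing censoring at the 30 mg to 15 mg switch.
- Do not map the 30-day follow-up sample to a scheduled visit. Show it as its own row, because a sample taken on day 30 would pass the filter.
- List values collected after the limit.

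The long-term significant-value and liver-elevation counts need no change on this account. For the completed Week 12 means and final-value shifts (SAP 10.3.2), a sensitivity re-run with the same filter is optional.

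The cost is a few lines of SAP text, one program filter and slightly fewer observations at late visits. Values up to 30 days off drug would still count, so some dilution remains, and a table footnote should say so.

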#### **8.1.5 Safety Analyses**

##### **8.1.5.1 General Considerations**

Safety analyses will be carried out using the Safety Analysis Set. Analyses will be conducted for Period 1 alone, as well as for Period 1 and Period 2 combined.

Safety analyses are based on treatments actually received. Safety will be assessed by AEs, physical examination, laboratory assessments, ECG, and vital signs. Frequency tables and lists of subjects with treatment-emergent AEs by preferred term as in the Medical Dictionary for Regulatory Activities (MedDRA) dictionary, by system organ class, by severity, and by relationship to the study drug as assessed by the Investigator will be provided. The changes from baseline in vital signs, physical examination results, and clinical laboratory values will be analyzed in a descriptive manner. Shift of laboratory values from baseline to defined time points will be tabulated.

Missing safety data will not be imputed.

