#### **8.1.5.3 Analysis of Laboratory, Vital Sign, and ECG Data**

Changes from baseline by visit, and changes from baseline to minimum value, maximum value, and final values in continuous laboratory data, and vital signs will be summarized by treatment group.

Baseline values are defined as the last non-missing measurements recorded on or before the date of the first dose of study drug in Period 1.

The laboratory data will be categorized as Grade 1, Grade 2, Grade 3, and Grade 4 according to OMERACT criteria (Rheumatology Common Toxicity Criteria v.2.0). For creatine phosphokinase and serum creatinine, NCI CTC criteria will be used. The shift tables will tabulate the number and percentage of subjects with baseline and post-baseline values by grade level.

Listings will be provided for potentially clinically significant laboratory values and vital signs.

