### **Mixed Effect Model Repeat Measurement (MMRM) for Short-Term Analysis**

The repeated measure analysis will be conducted using mixed model including observed measurements at all visits. The mixed model includes the categorical fixed effects of treatment, visit and treatment-by-visit interaction, main stratification factors at randomization and the continuous fixed covariates of baseline measurement. An unstructured variance covariance matrix will be used. The parameter estimations are based on the assumption of data being missing at random and using the method of restrictive maximum likelihood (REML). The missing at random assumption is considered reasonable given the high placebo response rate typically seen in RA trials. Additionally in RA trials, the proportion of discontinuation is relatively small (10 – 15% only) and the rate of discontinuation due to lack of efficacy is generally low (< 5%).

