### **9.2.3 Key Secondary Efficacy Analyses**

Ranked key secondary endpoints (at Week 12) for US/FDA regulatory purposes are:

1. Change from baseline in DAS28 (CRP);
2. Change from baseline in HAQ-DI;
3. LDA as measured by DAS28 (CRP);
4. Change from baseline in SF-36 Physical Component Score (PCS).

Ranked key secondary endpoints (at Week 12) for EU/EMA regulatory purposes are:

1. Change from baseline in DAS28 (CRP);
2. ACR20 response rate;
3. Change from baseline in HAQ-DI;

4. Change from baseline in SF-36 Physical Component Score (PCS).

Other key secondary endpoints (at Week 12) for both US/FDA and EU/EMA regulatory purposes are:

1. ACR50 response rate;
2. ACR70 response rate;
3. ACR20 response rate at Week 1.

For binary endpoints, frequencies and percentages will be reported for each randomized treatment group. Similar analyses as for the primary endpoint will be conducted.

For the major RA continuous endpoints DAS28 and HAQ-DI change from baseline, statistical inference will be conducted using analysis of covariance (ANCOVA) coupled with MI for missing data handling. Specifically, the ANCOVA model will include treatment as the fixed factor, and the corresponding baseline value and the stratification factor prior bDMARD use (Yes/No) as the covariates. For other continuous endpoints, statistical inference will be conducted using the MMRM model as described in Section 9.1.2, with the main stratification factor being prior bDMARD use (Yes/No). From both the MI and MMRM analyses, the LS mean and 95% CI will be reported for each randomized treatment group; the LS mean treatment difference and associated 95% CI and p-value will be reported comparing each Upadacitinib dose group with the combined placebo group. Both nominal p-value and adjusted p-value through the graphical multiplicity procedure described in Section 9.2.5 will be provided.

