## **10.2.1 Analysis of Adverse Events Prior to Protocol-Defined Treatment Switching**

### **10.2.1.1 Adverse Events Overview**

The number and percentage of subjects experiencing TEAEs will be summarized by "as treated" treatment group and overall for the following AE categories.

- All TEAEs
- Treatment-emergent serious adverse events (SAEs)
- Treatment-emergent severe adverse events
- TEAEs reasonably possibly related to study drug
- TEAEs of special interest
- TEAEs leading to discontinuation of study drug
- TEAE leading to death

In the AE overview summary, any event with an unknown severity will be considered as severe and any AE with an unknown relationship will be considered as having "reasonable possibility" of being related to study drug.

Additional AEs may be considered for tabulation/summary based on recommendations from Clinical and Safety as deemed appropriate.

For TEAEs of special interest, the point estimate and 95% CI (using normal approximation) will be provided for the treatment difference in AE percentage between each Upadacitinib dose group and the combined placebo group.

As a sensitivity analysis, the AE overview summary will be repeated by randomized treatment groups (Upadacitinib 15 mg QD, Upadacitinib 30 mg QD and the combined placebo groups). In this summary, all AEs with an onset date after the first dose of study drug will be included, regardless of whether the AE occurred more than 30 days after the last dose of study drug.

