### **10.3.2.3 Assessment of Potentially Clinical Significant Laboratory Values**

The criteria for potentially clinically significant laboratory values will be determined by OMERACT criteria of Grade 3 or 4. For creatine phosphokinase and creatinine, NCI CTC criteria will be used.

The number and percentage of subjects meeting the criteria for potentially clinically significant laboratory values will be summarized by "as treated" treatment group and overall. Comparisons of the percentage of subjects experiencing a value meeting the criteria between treatment groups will be performed using Fisher's exact tests. Only p-values  $\leq 0.100$  when rounded to three digits will be presented.

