**Table 10. Criteria for Potentially Clinically Significant Vital Sign Findings**

Vital Sign	Category	Criteria for Potential Clinically Significant Vital Signs
Systolic blood pressure	Low	Value $\leq$ 90 mmHg and decrease $\geq$ 20 mmHg from Baseline
	High	Value $\geq$ 160 mmHg and increase $\geq$ 20 mmHg from Baseline
Diastolic blood pressure	Low	Value $\leq$ 50 mmHg and decrease $\geq$ 15 mmHg from Baseline
	High	Value $\geq$ 105 mmHg and increase $\geq$ 15 mmHg from Baseline
Weight	High	> 7% increase from baseline
	Low	> 7% decrease from baseline

#### 10.4.2 Analysis of Vital Sign by Week 12

Analyses of mean change from baseline in continuous vital sign variables which are measured longitudinally will be performed by visits and by the "as treated" treatment groups of Upadacitinib 15 mg QD, Upadacitinib 30 mg QD, and combined placebo groups. For each change from baseline analysis, the following summary statistics will be presented for each treatment group: sample size, baseline mean, visit mean, and the mean, standard deviation, and median of the changes from baseline. An ANOVA model with treatment as factor, will be used to test statistical significance for the change from baseline mean among different treatment groups.

The number and percentage of subjects meeting the criteria for potentially clinically significant vital sign values will be summarized by "as treated" treatment group and overall.

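### Week 12 tests of mean change in labs and vital signs omit the baseline value; including it would usually make them more sensitive

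*SAP*

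**What the plan says.** SAP 10.3.2.1 summarises change from baseline in continuous hematology, chemistry and urinalysis variables by visit and as-treated group, and adds a test: "An ANOVA model with treatment as a factor will be used to test statistical significance for the change from baseline mean". SAP 10.4.2 does the same for vital signs: "An ANOVA model with treatment as factor, will be used to test statistical significance for the change from baseline mean among different treatment groups". The groups are 15 mg, 30 mg and combined placebo. Neither section names a baseline covariate, an adjusted sensitivity analysis, or a dose-versus-placebo mean difference with an interval.

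The SAP's continuous efficacy models do adjust for baseline. The short-term MMRM (SAP 9.1.2) includes "main stratification factors at randomization and the continuous fixed covariates of baseline measurement". For DAS28 and HAQ-DI (SAP 9.2.3), "the ANCOVA model will include treatment as the fixed factor, and the corresponding baseline value" is specified.

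The protocol asks for less. Section 8.1.5.1 states: "The changes from baseline in vital signs, physical examination results, and clinical laboratory values will be analyzed in a descriptive manner". Section 8.1.5.3 lists summaries by group, including "changes from baseline to minimum value, maximum value, and final values in continuous laboratory data", and names no test.

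**The concern.** An ANOVA on change scores subtracts the whole baseline value, which amounts to assuming a slope of exactly 1 between follow-up and baseline. Where the true slope differs, part of the baseline variation stays in the error term and the test loses sensitivity. The baseline value is already part of every change score, so leaving it out of the model saves nothing in data collection.

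The placebo comparison ends at Week 12, and the long-term lab and vital-sign sections (SAP 10.3.3.1 and 10.4.3) contain no test of mean change. A modest mean shift that crosses no toxicity grade is what these Week 12 tests are best placed to show. At stake is the chance of seeing such a shift in a supportive safety analysis.

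**Working it through.** **The plan's own figure.** The documents state no power for these tests. The only stated power is about 90% for the two primary endpoints, with 450 subjects and 10% dropout (SAP 4.3). Pooling placebo gives 150 per arm, and 150 × 0.9 = 135. A two-proportion normal test at two-sided 0.025 with 135 per arm gives 88% for 27% versus 47% and 89% for 12% versus 29%. Both agree with the stated figure, so 135 per arm is used below.

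**Assumptions, none in the documents.** ρ is the baseline-to-follow-up correlation and k is follow-up SD divided by baseline SD. Effects are in baseline SDs and tests are two-sided at 5%.

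**Formulas.**
- Variance of a change score: 1 + k² − 2ρk.
- Variance after baseline adjustment: k²(1 − ρ²).
- The first minus the second is (1 − ρk)². It is never negative, and it is zero only when the slope ρk equals 1.
- SE of a pairwise difference: √(variance × 2/135). For ANCOVA the variance is multiplied by 1 + 1/(405 − 5) = 1.0025, the cost of estimating the slope.
- Difference detectable with 80% power: (1.966 + 0.842) × SE = 2.808 × SE.

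**Example, k = 1 and ρ = 0.5.** The change variance is 1 + 1 − 1 = 1.00, so SE = √(2/135) = 0.122. The adjusted variance is 0.75 × 1.0025 = 0.752, so SE = 0.106. The reduction is 13%.

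**Equal SDs (k = 1).**

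| ρ | SE, ANOVA to ANCOVA | SE reduction | Detectable difference (SD) |
|---|---|---|---|
| 0.3 | 0.144 to 0.116 | 19.3% | 0.404 to 0.326 |
| 0.5 | 0.122 to 0.106 | 13.3% | 0.342 to 0.296 |
| 0.7 | 0.094 to 0.087 | 7.7% | 0.265 to 0.244 |
| 0.9 | 0.054 to 0.053 | 2.4% | 0.153 to 0.149 |

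**Unequal SDs, SE reduction at ρ = 0.3, 0.5, 0.7, 0.9.**
- k = 1.25: 11.3%, 5.4%, 0.8%, 2.4%. At ρ = 0.8 the slope is 1.25 × 0.8 = 1 and the change is −0.1%.
- k = 0.8: 29.1%, 24.3%, 20.7%, 21.9%.

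**Three-group F test.** This is the test the SAP specifies. Assume shifts of 0, 0.15 and 0.30 SD (placebo, 15 mg, 30 mg). The squared deviations from their mean sum to 0.045, so the noncentrality is 135 × 0.045 = 6.075 divided by the variance, with 2 and 402 (ANOVA) or 401 (ANCOVA) degrees of freedom. At k = 1, power goes from 44% to 63%, 59% to 72%, 82% to 88% and 99.9% to 100% across the four correlations. These figures describe the global test. For pairwise contrasts, only the SEs and detectable differences apply.

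**Skewed data and validity.** With lognormal data (log-SD 0.8, 4,000 simulated trials per setting), F-test power goes from 34% to 47%, 44% to 53%, 63% to 68% and 97% to 97%. Under the null, rejection was 4.4% to 5.4% for ANOVA and 4.4% to 5.6% for ANCOVA across normal and lognormal data.

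**The case against.** The strongest reply is that nothing here is an error. The unadjusted ANOVA is valid and reads directly beside the raw mean changes in the same table. The protocol promises only description, so the SAP's test already goes beyond it. Other screens cover safety: special-interest event comparisons ("the treatment difference in AE percentage between each Upadacitinib dose group and the combined placebo group", with intervals), shift tables, liver criteria, and Fisher's exact tests on Grade 3 or 4 values ("Comparisons of the percentage of subjects experiencing a value meeting the criteria between treatment groups will be performed"). Period 1 was reported under SAP version 2.0, so any adjusted analysis would now be post hoc. The size of the gain also rests on assumed inputs. All of this stands and limits the weight of the point. It does not remove it: those screens rely on events or thresholds, not mean shifts, and adjustment costs one degree of freedom.

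Four stronger readings are tempting, and the documents do not support them.
- **The tests are biased or have inflated type I error.** They are not, provided the as-treated groups essentially match the randomised ones.
- **No laboratory mean change is tested against placebo with baseline adjustment.** hs-CRP is in the SAP's laboratory list and is also an ACR component, so its change is tested by a baseline-adjusted MMRM (SAP 9.2.4 and Table 4). Protocol 8.1.7 plans a baseline-adjusted comparison of lymphocyte subsets.
- **Adjusting efficacy but not safety models is a contradiction.** It is a difference in approach; the ranked efficacy endpoints carry confirmatory inference.
- **The F-test power gains carry over to each dose-versus-placebo contrast.** They do not, because they describe the three-group test.

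**Conclusion.** The point holds as a modest, optional improvement. For hematology, chemistry, urinalysis and vital-sign variables, the Week 12 mean-change tests are valid but usually less sensitive than they could be. The loss is in precision only. It is material if correlations are low to moderate, or if follow-up values vary less than baseline. It is negligible at a correlation of 0.9 with equal SDs, and absent where the slope is 1. All sizes rest on assumed correlations, SD ratios and shifts; only the 135 per arm derives from the documents. The results do not carry over to percentage change in LDL, HDL and cholesterol, which SAP 10.3.2.1 also analyses. Sample size and the primary and ranked key secondary conclusions are unaffected.

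**What to change.** In SAP 10.3.2.1 and 10.4.2, replace the treatment-only ANOVA on absolute change with an ANCOVA that has treatment as factor and the baseline value as covariate. Report the LS mean difference and 95% confidence interval for each dose versus combined placebo, with p-values labelled exploratory.

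Because Period 1 reporting is complete (SAP 11.1 and Appendix B), present this as a labelled post hoc supplement at Week 12 beside the reported ANOVA. Limit it to:
- hemoglobin, neutrophils, lymphocytes, ALT, AST, creatinine and CPK, which relate to the events of special interest in Protocol 6.1.1.3;
- absolute LDL and HDL, because Protocol 3.0 reports lipid increases in Phase 2;
- systolic and diastolic blood pressure, a judgement based on closeness to the cardiovascular events, since blood pressure is not itself on that list.

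Consider a log scale for skewed variables such as CPK. Make no precision claim for percentage change in lipids.

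The cost is one model term per variable and 11 × 2 = 22 contrasts, plus the extra tables. By comparison, all 34 hematology and chemistry variables and 6 vital signs at Weeks 2, 4, 8 and 12 would need 40 × 4 × 2 = 320 contrasts, before any urinalysis. The long-term summaries need no change. No new data or patient burden is involved.
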